15.9. Investigator Training

Device, protocol and electronic database training will be provided to the appropriate personnel prior to patient enrollment in the trial. Device training will be conducted at the TransMedics clinical training facility or equivalent training facility. Protocol training will include a thorough review of this protocol. Electronic database training will consist of an explanation of the structure of the database, the data elements to be collected, simulated use of the database, error handling, and instructions regarding the handling of queries.

17. AMENDMENT POLICY

The investigator will not make any changes to this protocol without prior written consent from the Sponsor and subsequent approval by the IRB or EC, except if the deviation from the protocol is necessary to protect the life and physical well-being of a subject in an emergency. Such protocol deviations will be reported to the Sponsor and the reviewing IRB or EC as soon as possible, but no later than 5 working days after the emergency occurred. Protocol amendments will be submitted to

the chairman of the IRB responsible for reviewing amendments. Except for “administrative letters,” investigators will await IRB approval of protocol amendments before implementing the change(s).

15. Mancini, D. and Lietz, K. Selection of Cardiac Transplantation Candidates in 2010. *Circulation*; 2010; 122:173-183.

16. Messer, et al. Outcome after Heart Transplantation from Donation after Circulatory-determined Death Donors. *J. Heart. Lung Transplant*; 2017, 36(12):1311-1312.
17. Nicoara, et al. Primary Graft Dysfunction after Heart Transplantation: Incidence, Trends and Associated Risk Factors. *Am. J. Transplant.*; 2018; 18:1461-1470.
18. Peura, et al. on behalf of the American Heart Association Heart Failure and Transplantation Committee, Recommendations for the Use of Mechanical Circulatory Support: Device Strategies and Patient Selection: A Scientific Statement from the American Heart Association. *Circulation*; 2012; 126:2648-2667.
19. Squiers, et al. Application of the International Society for Heart and Lung Transplantation (ISHLT) criteria for Primary Graft Dysfunction after Cardiac Transplantation: Outcomes from a High-Volume Centre. *Euro. J. Cardio-Thoracic Surg*; 2017, 51:263-270.
20. Wilhelm, M.J. Long term outcome following heart transplantation: Current Perspective. *J. Thoracic Dis.*; 2015; 7(3):549-551.

APPENDIX 1. ISHLT CONSENSUS MANUSCRIPT HEART PRIMARY GRAFT DYSFUNCTION (PGD) (KOBASHIGAWA, ET AL., 2014)

Table 6 Definition of Severity Scale for Primary Graft Dysfunction (PGD)

1. PGD-Left ventricle (PGD-LV):	Mild PGD-LV: One of the following criteria must be met:	LVEF \leq 40% by echocardiography, or Hemodynamics with RAP $>$ 15 mm Hg, PCWP $>$ 20 mm Hg, CI $<$ 2.0 L/min/m ² (lasting more than 1 hour) requiring low-dose inotropes
	Moderate PGD-LV: Must meet one criterion from I and another criterion from II:	I. One criteria from the following: Left ventricular ejection fraction \leq 40%, or Hemodynamic compromise with RAP $>$ 15 mm Hg, PCWP $>$ 20 mm Hg, CI $<$ 2.0 L/min/m ² , hypotension with MAP $<$ 70 mm Hg (lasting more than 1 hour) II. One criteria from the following: i. High-dose inotropes—Inotrope score $>$ 10 ^a or ii. Newly placed IABP (regardless of inotropes)
	Severe PGD-LV	Dependence on left or biventricular mechanical support including ECMO, LVAD, BiVAD, or percutaneous LVAD. Excludes requirement for IABP.
2. PGD-right ventricle (PGD-RV):	Diagnosis requires either both i and ii, or iii alone:	i. Hemodynamics with RAP $>$ 15 mm Hg, PCWP $<$ 15 mm Hg, CI $<$ 2.0 L/min/m ² ii. TPG $<$ 15 mm Hg and/or pulmonary artery systolic pressure $<$ 50 mm Hg, or iii. Need for RVAD

BiVAD, biventricular assist device; CI, cardiac index; ECMO, extracorporeal membrane oxygenation; IABP, intra-aortic balloon pump; LVAD, left ventricular assist device; PCWP, pulmonary capillary wedge pressure; RAP, right atrial pressure; RVAD, right ventricular assist device; TPG, transpulmonary pressure gradient.

^aInotrope score = dopamine ($\times 1$) + dobutamine ($\times 1$) + amrinone ($\times 1$) + milrinone ($\times 15$) + epinephrine ($\times 100$) + norepinephrine ($\times 100$)⁶⁷ with each drug dosed in μ g/kg/min.

Note: All incidences of PGD will be adjudicated by the CEC.

Hemodynamic data will be used in the assessment of PGD severity only if collected by centers as clinically indicated, per the institution's standard of care. This approach is consistent with contemporary U.S. publications on PGD using ISHLT criteria (Nicoara, et al., 2018; Squiers, et al., 2018). If hemodynamic data are not collected, the CEC will use available clinical data to adjudicate PGD severity grading.

APPENDIX 2. SCHEDULE OF CLINICAL ASSESSMENTS

Evaluations	Donor & Heart Assessments	
	Acceptance	OCS Preservation
Eligibility & ID	X	
Demographics/Characteristics	X	
Donor Cause of Death	X	
Donor Medical & Social History	X	
Donor Heart Assessment	X	
Donor Cross Clamp Time	X	
OCS Preservation Parameters		X
OCS Lactate Levels		X
Device Malfunction (if applicable)		X
Non-transplant Reasons (if applicable)		X

Evaluations	DCD Transplanted Recipient Schedule of Assessments							
	Day of Tx	T0 ^a	T24	T72	Initial Hospital Discharge	Day 30	Mo 6 ^c	Mo 12 ^d
Eligibility & Informed Consent	X							
Demographics/ Characteristics	X							
Medical & Cardiac History	X							
Transplant Details	X							
PGD Scores			X					
Inotropic Support		X	X					
Right Heart Catheter Results		X ^b	X ^b					
Mechanical Circulatory Support		X	X	X				
Patient & Graft Survival		X	X	X	X	X	X	X
Echocardiogram			X					
Initial ICU Stay						X		
Initial Hospital Stay						X		
HGRSAEs and SAEs	X	X	X	X		X		
Cardiac Allograft Vasculopathy								X ^b

a T0 is defined as the time of initial admission to ICU immediately post-heart transplant procedure

b ONLY Tests regularly scheduled per center standard of care or performed due to a clinical cause at these timepoints will be collected.

c Six month follow-up window is \pm 30 days

d Twelve month follow-up window is \pm 60 days

APPENDIX 4. DRAFT ELECTRONIC CASE REPORT FORMS

(This Page is Intentionally Left Clear)

## List of Abbreviations

Term	Definition
BiVAD	Bilateral Ventricular Assist Device
BMI	Body Mass Index
BTT	Bridge to Transplant
CEC	Clinical Events Committee
CI	Confidence Interval
DBD	Donor after Brain Death
DCD	Donor after Circulatory Death
ECMO	Extracorporeal Membrane Oxygenation
EVHP	Ex-Vivo Heart Perfusion
HGRSAE	Heart Graft-Related Serious Adverse Event
IABP	Intra-aortic Balloon Pump
ICU	Intensive Care Unit
ISHLT	International Society for Heart and Lung Transplantation
LVAD	Left Ventricular Assist Device
MCS	Mechanical Circulatory Support
MedDRA	Medical Dictionary for Regulatory Activities
mITT	modified Intent-to-treat
OCS	Organ Care System
OPTN	Organ Procurement and Transplantation Network
PGD	Primary Graft Dysfunction
PMA	Premarket Approval
RVAD	Right Ventricular Assist Device
SAE	Serious Adverse Event
SBP	Systolic Blood Pressure
SD	Standard Deviation
SOC	Standard of Care
T0, T24, T72	Time after transplant (0, 24, 72 hours)
UNOS	United Network for Organ Sharing
US	United States
WIT	Warm Ischemic Time

## **1.0 INTRODUCTION**

This analysis plan provides a detailed description of the safety and effectiveness analyses (and associated summary tables) planned in the analysis of data in the OCS-CAR-03202019 study “Clinical Trial to Evaluate the Safety and Effectiveness of The Portable Organ Care System (OCS™) Heart for Resuscitation, Preservation and Assessment of Hearts from Donors after Circulatory Death (DCD Heart Trial)”.

## **2.0 STUDY OBJECTIVE**

The objective of the DCD Heart Trial is to evaluate the effectiveness of the OCS Heart System to resuscitate, preserve, and assess hearts donated after circulatory death for transplantation, and to ultimately increase the pool of donor hearts available for transplantation.

[figure not shown]
A secondary objective is to evaluate the safety and effectiveness of transplanting DCD hearts preserved on the OCS Heart System compared to transplantation with Donor after Brain Death (DBD) hearts preserved with SOC.

## 3.0 STUDY DESIGN

### 3.1 Overview

This is a prospective, randomized and concurrent controlled, non-inferiority pivotal trial in which subjects who receive a DCD donor heart transplant will be compared to subjects who receive a standard of care (SOC) donor heart transplant, regardless of whether those subjects were randomized to receive an SOC donor heart (SOC1) or to potentially receive a DCD donor heart (SOC2). The primary effectiveness comparison between these groups is analyzed by actual treatment and includes adjustment for differences in risk factors. The trial design is illustrated in Figure 1 below.

**Figure 1: DCD Heart Trial Design**

The trial will be conducted at a maximum of 25 participating sites with 90 transplanted DCD heart recipients and 90 SOC heart transplant recipients. Follow-up data for the SOC recipients will be obtained from the UNOS/OPTN standard database for U.S. transplant recipients through five years after transplantation.

Subjects who receive a DCD heart transplant will be followed for 12 months from the date of transplantation. Data from UNOS/OPTN transplantation database will be obtained through five years after transplant.

The Schedule of Clinical Assessments for the donor and recipient is provided in Table 1.

**Table 1. Schedule of Clinical Assessments**

Evaluations	Donor & Heart Assessments	
	Acceptance	OCS Preservation
Eligibility & ID	X	
Demographics/Characteristics	X	
Donor Cause of Death	X	
Donor Medical & Social History	X	
Donor Heart Assessment	X	
Donor Cross Clamp Time	X	
OCS Preservation Parameters		X
OCS Lactate Levels		X
Device Malfunction (if applicable)		X
Non-transplant Reasons (if applicable)		X

Evaluations	DCD Transplanted Recipient Schedule of Assessments							
	Day of Tx	T0 a	T24	T72	Initial Hospital Discharge	Day 30	Mo 6 c	Mo 12 d
Eligibility & Informed Consent	X							
Demographics/ Characteristics	X							
Medical & Cardiac History	X							
Transplant Details	X							
PGD Scores			X					
Inotropic Support		X	X					
Right Heart Catheter Results		X b	X b					
Mechanical Circulatory Support		X	X	X				
Patient & Graft Survival		X	X	X	X	X	X	X
Echocardiogram			X					
Initial ICU Stay					X			
Initial Hospital Stay						X		
HGRSAEs and SAEs	X	X	X	X			X	
Cardiac Allograft Vasculopathy								X b

a T0 is defined as the time of initial admission to ICU immediately post-heart transplant procedure.  
b ONLY Tests regularly scheduled per center standard of care or performed due to a clinical cause at these timepoints will be collected.  
c Six month follow-up window is  $\pm$  30 days.  
d Twelve month follow-up window is  $\pm$  60 days.

### 3.2 Method of Assigning Subjects to Treatment

Primary heart transplant candidates will be screened for trial eligibility. Every eligible candidate will be asked to participate. Consented subjects will be randomized into two groups: ***DCD Heart Possible*** and ***SOC Heart Only***.

Subjects who are randomized into the ***SOC Heart Only*** group will have no possibility for a DCD Heart transplant. Subjects randomized into the ***DCD Heart Possible*** group have the possibility of receiving either a DCD heart or an SOC donor heart, depending upon the donor match. In order to obtain enough subjects with DCD donor heart transplants, subjects will be randomized 3:1 to the ***DCD Heart Possible*** and ***SOC Heart Only*** arms, respectively. Eligible subjects in the ***SOC Heart Only*** group who are transplanted will form one ***SOC Heart Transplanted Recipient group (SOC1)***. In the ***DCD Heart Possible*** arm, if a screened and eligible subject is matched with an SOC donor heart before an eligible DCD donor heart becomes available and is transplanted, these subjects will form a second ***SOC Heart Transplanted Recipient group (SOC2)***.

Note: After completing enrollment there were 6 cases in which a SOC donor heart was transplanted without randomization. These subjects' data will be included in data listings and in ad-hoc analyses to support the final clinical study report.

### 3.3 Blinding

This is an open label study. However, the SOC 6-month primary endpoint survival data will be blinded to the statistical group until the database hard-lock.

### 3.4 Determination of Sample Size

We have assumed that transplantation of a DCD donor heart will be an infrequent event and that there will be at least a 1:1 ratio of SOC heart transplants to DCD heart transplants, despite the 3:1 randomization to the ***DCD Heart Possible*** and ***SOC Heart Only*** groups. The sample size calculations were based on the following specifications:

- Non-inferiority study with comparison of DCD heart transplanted recipients to SOC heart transplanted recipients
- Primary endpoint is patient survival at 6 months post-transplant
- One-sided normal approximation test
- Alpha = 0.05
- Power = 80%
- Assume 1:1 occurrence of SOC heart transplants (SOC1 and SOC2) and DCD heart transplants
- True SOC survival percentage = 93%
- True DCD survival percentage = 85%
- Non-inferiority margin = 20%.

Based on these assumptions, a sample size of 84 DCD heart transplanted recipients and at least 84 SOC heart transplanted recipients will provide at least 80% power. This sample size was increased to

90 per group to reflect potential enrollment of subjects who are lost to follow-up, withdraw or do not meet eligibility criteria.

### **3.5 Changes to the Protocol-Specified Analyses**

The protocol proposed stopping enrollment once the DCD heart transplanted recipients enrollment target (N=90) was met. Further, if the enrollment target in the SOC heart transplanted recipient population had not been met, a propensity-score-matched subset of subjects from the UNOS database was proposed to supplement the set of subjects in the SOC Heart Transplanted Recipient Population at the time of the last DCD transplant. However, in communications with FDA it became clear that FDA strongly preferred prospective enrollment of 90 SOC subjects rather than the propensity matched approach outlined in the protocol. Therefore, the statistical analysis will be performed using the 90 DCD and 90 SOC subjects that were prospectively enrolled without propensity-matched subjects from UNOS.

The protocol stated that the analysis of the primary effectiveness endpoint would be adjusted for known donor and recipient risk factors (defined in section 12.1) for mortality, and any of the baseline and demographic characteristics identified as potential risk factors for which there is a statistically significant difference between the treatment groups. This SAP clarifies that the primary effectiveness analysis will be adjusted for known donor and recipient risk factors for mortality, but not for baseline and demographic characteristics identified as potential risk factors.

The protocol stated that statistical testing will be performed for the comparisons of recipient demographics and baseline characteristics and of patient survival at 6 months for the following groups: SOC1 vs SOC2, DCD Heart vs SOC1, DCD Heart vs SOC2. Only summary statistics will be provided for those comparisons.

[figure not shown]
Sensitivity analyses of the primary effectiveness endpoint were not described in the protocol and have been added to the SAP. First, an unadjusted analysis will be performed with the same non-inferiority margin as recommended by the FDA. Additionally, a tipping point analysis will be performed without risk factor adjustment using the Wald method, in which subjects with unsuccessful or missing outcomes in the SOC Heart Transplanted Recipient Population will have successful outcomes imputed iteratively. The primary effectiveness endpoint will also be analyzed using Kaplan Meier methods. Per FDA's request, a sensitivity analysis was added to compare the primary effectiveness by randomization (i.e., to compare the DCD Heart Possible Population vs. the SOC Heart Only Population).

The protocol defines the secondary effectiveness endpoint (DCD donor heart utilization rate) as the number of eligible DCD donor hearts that met the warm ischemic time (WIT) limit ( $\leq 30$  mins) and were instrumented on the OCS Heart System that meet the acceptance criteria for transplantation after OCS Heart preservation divided by the total number of eligible DCD donor hearts that met the warm ischemic time limit above and were instrumented on the OCS Heart System (i.e., based on the OCS Heart Population). It is clarified in the SAP that this is the primary analysis of the secondary effectiveness endpoint. The utilization rate based on the modified OCS (mOCS) Heart Population is added in the SAP, defined as the number of DCD hearts that were successfully transplanted after preservation and assessment on the OCS divided by the total number of DCD donor hearts that were instrumented on the OCS.

The protocol defines post-transplant mechanical circulatory support (MCS) as LVAD, RVAD, and BiVAD. The list of MCS was updated to also include ECMO, TAH, and IABP. For the study endpoint of use of post-transplant MCS for > 72 hours immediately post-transplant, it was clarified that only post-transplant MCS that is initiated within the initial 24 hours (T24 visit) post-OR discharge with an implant duration of greater than 72 hours will be considered to meet this study endpoint. This was proposed to avoid double counting IABP that was inserted pre-transplant and stayed for 1-2 days until the patient clotting factors are stabilized post-transplant.

Pre-transplant IABP (regardless of indication) that is removed per standard of care a couple of days post-transplant will be excluded from any post-transplant MCS analysis. Pre-transplant IABP that is maintained during transplantation and restarted for post-transplant cardiac support, and any IABP placed post-transplantation will be considered as newly placed IABP and included in the MCS endpoint analysis. Additionally, the newly placed IABP will be summarized by its indication as shown in the Figure 2 below. These IABP categories and indications will be adjudicated by the CEC.

**Figure 2. Inclusion of IABP in Post-transplant (Post-Tx) MCS Analysis**

Primary Graft Dysfunction (PGD) data for SOC patients (SOC1+ SOC2) will be collected from the investigational sites and adjudicated by CEC according to the ISHLT criteria. The ISHLT PGD will be summarized for the SOC patients based on CEC adjudication and will be compared to the DCD heart transplanted patients using descriptive statistics.

The patient survival, graft survival and hospital discharge information will be collected for SOC patients from the UNOS/OPTN database. The graft survival of SOC patients will be analyzed following CEC adjudication. Per the UNOS/OPTN Heart TRR form, graft failure includes heart re-transplantation and the cardiac-graft related death. Deaths that are a result of some other factor unrelated to graft failure are not included in this endpoint.

Number of HGRSAEs will be calculated for SOC patients by combining ISHLT moderate or severe PGD and primary graft failure requiring re-transplantation within the first 30 days post-transplant. HGRSAEs for the SOC patients will be compared to the DCD heart transplanted patients.

In summary, other endpoints were added, including:

- Patient and graft survival at 30 days post-transplant for SOC patients.
- Patient and graft survival at 30 days or initial hospital discharge, if later than 30 days for SOC patients.
- ISHLT moderate-severe PGD (left or right ventricle) (not including rejection or cardiac tamponade) within 24 hours according to ISHLT consensus manuscript (as defined in Appendix 1 of the protocol) for both OCS and SOC patients.
- ISHLT severe PGD (left or right ventricle) (not including rejection or cardiac tamponade) within 24 hours according to ISHLT consensus manuscript (as defined in Appendix 1 of the protocol) for SOC patients.
- HGRSAEs for SOC patients, consisting of ISHLT moderate or severe PGD and primary graft failure requiring re-transplantation within 30 days post-transplant.
- Kaplan-Meier estimated patient and graft survival at 30, 180, and 365 days post-transplant for both OCS and SOC patients.

A site poolability analysis for the primary efficacy endpoint was added for the DCD/SOC Heart Transplanted Recipient Population and for the DCD-mITT/SOC m-ITT Heart Transplanted Recipient Population.

Subgroup analyses of survival and severe ISHLT PGD endpoints were added for the DCD Heart/DCD-mITT Population. The subgroups will be based on WIT (0 - 20 minutes vs. >20 - 30 minutes vs. >30 minutes).

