- The incidence of ISHLT severe PGD was 10.7%, and the incidence of ISHLT moderate or severe PGD was 14.7%. These rates compare favorably with contemporary literature reporting PGD rates post-heart transplantation using the ISHLT criteria.
- Survival at 30 days, 6 months, and 12 months was 95%, 88%, and 84%, respectively.
- The FDA also approved a Continued Access Protocol (CAP) for EXPAND called the EXPAND CAP. The study is on-going and data are still being collected, but based on the available data the results show:
 - 38 donor hearts were preserved and assessed on the OCS Heart System.
 - The utilization rate is 89.5%, with 34 of 38 extended criteria donor hearts successfully transplanted.
 - The first 20 transplanted patients have reached a minimum of 30-day follow-up and all survived (100% survival at 30-days).
 - No severe LV or RV ISHLT PGD has been reported among the first 20 subjects transplanted.
- PROCEED II was the first pivotal study of the OCS Heart System. It was a randomized study of the OCS Heart System compared to standard of care cold storage, and it enrolled standard criteria donor hearts. The study met its primary endpoint and non-inferiority was shown in 30-day survival, as well as in the secondary endpoint, i.e., cardiac graft-related SAEs. Longer-term data, obtained from the SRTR database, showed lower survival rates for the OCS group at 2-3 years of follow-up; however, the incidence of cardiac graft-related deaths was similar and other deaths were typical for heart transplant recipients (late infection, malignancy, multi-organ failure). The results of this study were published in the Lancet (Ardehali, et al., 2015).
- Studies of the OCS Heart System for preservation of standard criteria donor hearts conducted outside the U.S. at hospitals in Germany and the UK showed improved rates of survival and lower rates of PGD for OCS compared to standard of care cold storage (Koerner, et al., 2014).

2.5. Overall Summary of Clinical Data to Support Initiation of OCS Heart DCD Trial

In summary, studies of the OCS Heart System for the preservation of DCD hearts have been performed outside of the U.S. These studies have shown 77.8 - 86.7% utilization rate, with 90-day and 1-year survival comparable to outcomes obtained with standard criteria donor hearts preserved using cold storage standard of care.

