15.7. Clinical Events Committee (CEC)

The Sponsor will utilize an independent Clinical Events Committee (CEC) to provide individual serious adverse event adjudication for the trial. It is anticipated that the CEC will meet with the Sponsor on a periodic basis, or as needed, depending on the rate of patient accrual. The CEC will be guided by the CEC Charter; however, the primary responsibilities of the CEC are to:

- Review reportable serious adverse events, including PGD, that occur over the course of the trial and the subsequent classification of these adverse events as related to the device.
- Provide recommendations to extend the length of follow-up past 30 days post-transplant for a subject experiencing a serious adverse event.

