## **4.0 EFFECTIVENESS AND SAFETY ENDPOINTS**

All effectiveness and safety endpoints based on primary heart graft dysfunction (PGD) results and the patient graft failure will use the Clinical Events Committee (CEC) adjudicated results.

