Kaplan-Meier estimates for patient survival and graft survival (graft failure includes heart re-transplant and cardiac graft-related death) probabilities will be calculated for the SOC Heart Transplanted Recipient Population, the SOC-mITT Heart Transplanted Recipient Population, the DCD Heart Transplanted Recipient Population, and the DCD-mITT Heart Transplanted Recipient Population for the following time points: Day 30, Month 6, and Month 12. Of note, the Kaplan-Meier estimates will consider time as a continuous variable measured in days. The Month 6 and Month 12 timepoints will be considered to be 180 and 365 days post-transplantation, respectively. Re-transplanted patients will be censored at the day of re-transplantation. The estimated difference in survival probability (SOC – DCD) and its 90% confidence interval will also be presented at each of the three time points.

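### Graft survival leaves out deaths adjudicated as unrelated to the graft, and the Kaplan-Meier rule censors re-transplants, so the SOC - DCD graft difference depends on cause-of-death adjudication and can lose events the SAP itself defines as failures

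*SAP*

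**What the plan says.** Protocol 5.4 lists graft survival among the other endpoints without defining it. The definition appears in SAP 3.5, which attributes it to a UNOS/OPTN form. Re-transplantation and cardiac graft-related death are failures, and the text adds: "Deaths that are a result of some other factor unrelated to graft failure are not included in this endpoint".

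SAP 12.3 repeats this for the Kaplan-Meier analysis of all four DCD and SOC populations ("graft failure includes heart re-transplant and cardiac graft-related death"). It presents the SOC - DCD difference with a 90% confidence interval at Day 30, Month 6 and Month 12. The same paragraph censors re-transplanted patients on the day of re-transplantation and does not limit that rule to the patient-survival curves. SAP 7.0 likewise treats these patients as discontinued at that point.

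On who decides, SAP 4.0 says that endpoints based on "the patient graft failure will use the Clinical Events Committee (CEC) adjudicated results". On masking, SAP 3.3 says "This is an open label study" and describes one restriction only: "However, the SOC 6-month primary endpoint survival data will be blinded to the statistical group until the database hard-lock". Protocol 15.7 also gives the committee the task of "the subsequent classification of these adverse events as related to the device".

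On data sources, SOC recipients exit the study at transplant (Protocol 6.4), and their graft survival comes from UNOS/OPTN (SAP 3.5). DCD recipients have trial follow-up at 6 and 12 months (Protocol 8.3). SAEs are collected to Day 30 for DCD recipients only (SAP 13.0).

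**The concern.** A recipient who dies of a cause judged unrelated to the graft has no working graft, yet is not counted as a graft loss. In a standard Kaplan-Meier analysis a death that is not an event can only be censored, which treats the recipient as if a later graft failure were still possible. The resulting curve shows neither the proportion alive with a functioning graft nor the cumulative incidence of graft-related failure. For the 30-day and discharge percentages, the SAP does not say whether such a death counts as graft survival or leaves the denominator.

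The between-group difference then depends on how deaths are classified. The classification is made in an open-label trial and rests on registry data in one group and trial follow-up plus 30-day SAE records in the other. If the share of deaths called non-graft differs between groups for reasons of evidence or knowledge of treatment, the graft difference moves with it.

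The censoring rule is a separate fault. Applied to the graft curves, it removes re-transplantation, which the same paragraph names as a failure. Only graft-related deaths would remain as events.

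**Working it through.** **The plan's own figure.** The documents state no number for graft survival. Their only related figure is the sample size for 6-month patient survival (SAP 3.4): SOC 93%, DCD 85%, margin 20 points, one-sided alpha 0.05, power 80%.

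n = (1.645 + 0.842)² × (0.93 × 0.07 + 0.85 × 0.15) / (0.20 - 0.08)² = 83 per group after rounding up, against 84 stated. It reproduces, so 15% and 7% are the right planning mortalities. At 90 per group they imply 13.5 DCD and 6.3 SOC deaths.

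**Gap as a function of attribution.** Let fD and fS be the shares of deaths judged graft-related. The documents give neither, so both are assumptions. Re-transplants are set to zero.

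Graft-failure gap (DCD - SOC) = 15% × fD - 7% × fS

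| Deaths called non-graft | DCD failure | SOC failure | Gap (points) |
|---|---|---|---|
| none (all-cause) | 15.0% | 7.0% | 8.0 |
| 30% in both | 10.5% | 4.9% | 5.6 |
| 50% in both | 7.5% | 3.5% | 4.0 |
| 70% in both | 4.5% | 2.1% | 2.4 |
| 60% DCD, 40% SOC | 6.0% | 4.2% | 1.8 |
| 40% DCD, 60% SOC | 9.0% | 2.8% | 6.2 |

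The extremes are -7.0 points (no DCD death and every SOC death judged graft-related) and +15.0 points (the reverse). The last two rows show that unequal attribution can move the gap either way.

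**One death.** With 90 per group, re-attributing one death moves the gap by 1/90 = 1.1 points.

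**Illustration with whole counts.** Take 14 DCD and 6 SOC deaths among 90 each. The all-cause gap is 14/90 - 6/90 = 8.9 points (90% CI 1.3 to 16.5). If all 6 SOC deaths but only 6 of the 14 DCD deaths are judged graft-related, the gap is 0.0 (90% CI -6.1 to 6.1).

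**Censoring error alone.** The table uses simple proportions. To isolate the Kaplan-Meier error, assume proportional cause-specific hazards and half of deaths non-graft. Then 1 - KM for DCD is 1 - 0.85^0.5 = 7.8%, against a true incidence of 7.5%. For SOC it is 1 - 0.93^0.5 = 3.6%, against 3.5%. The error is about 0.3 points or less. In an extreme ordering of 14 DCD deaths, where all 7 non-graft deaths precede the 7 graft-related ones, it is 7/83 = 8.4% against 7/90 = 7.8%. Attribution matters far more than the estimator.

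**Re-transplantation.** SAP 12.3 lists it as a graft failure and then censors it. With 90 at risk, each event lost this way is worth roughly 1/90 = 1.1 points in its group. The documents give no expected number.

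**The case against.** The strongest defence is that little depends on this endpoint. Graft survival is an other endpoint with no hypothesis, margin or test. The primary endpoint is 6-month patient survival, and all-cause patient survival is reported beside graft survival at every time point (SAP 4.3 and 12.3). Re-transplants for primary graft failure in the first 30 days also appear among the heart graft-related SAEs for both groups (SAP 4.4). The definition is disclosed, linked to the SOC data source and applied to both groups. A smaller gap under equal attribution is what a cause-specific endpoint measures and is not in itself bias. All of this stands, and it limits the weight of the point.

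It does not rescue the rule as written. A definition shared by both groups does not make the contrast independent of adjudication, and a registry category does not justify censoring an event that the definition counts.

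A reader might go further in four ways that the documents do not support:

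- *The committee is unmasked.* This is an inference. The trial is open label and no committee masking is described, but its charter is not among the documents.
- *The records are unequal throughout.* The imbalance is clearest to Day 30. Later DCD follow-up may be by phone (Protocol 8.3), UNOS/OPTN data are obtained for DCD recipients too (Protocol 4.2), and SOC graft survival is also adjudicated, with SOC PGD data collected from sites (SAP 3.5).
- *Graft survival must exceed patient survival.* That holds only if non-graft deaths outnumber re-transplants counted as failures.
- *The definition favours DCD hearts.* Protocol 2.4 says of the sponsor's earlier randomized trial, after reporting lower OCS survival at 2-3 years: "however, the incidence of cardiac graft-related deaths was similar and other deaths were typical for heart transplant recipients". This shows that the two measures can diverge. It does not show misattribution, and it concerns standard criteria hearts over a longer period.

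**Conclusion.** The point holds for the graft-survival endpoint and goes no further. As written, deaths judged unrelated to the graft are not failures, the SOC - DCD graft difference depends on cause-of-death adjudication, and the censoring sentence conflicts with the failure definition beside it.

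At the plan's own mortality rates, the 8-point all-cause gap becomes 2.4 to 5.6 points when 30% to 70% of deaths in both groups are called non-graft. Those shares are assumptions and re-transplants are set to zero. The pure competing-risk error is small, about 0.3 points under proportional hazards. The direction of any bias cannot be determined from the documents, and the primary endpoint is not affected. The change should be made because it is nearly free and because the re-transplant rule, read literally, gives a wrong result.

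**What to change.** In SAP 3.5, 4.3 and 12.3:

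1. Define graft survival as freedom from re-transplantation or death from any cause, for both the percentages and the Kaplan-Meier curves.
2. State that re-transplantation is an event in the graft curves, and exempt those curves from the sentence that censors re-transplanted patients. Align SAP 7.0, so that discontinuation at re-transplantation does not remove the event.
3. Keep graft-related failure under the UNOS-based definition as a supportive result. Estimate it as a cumulative incidence (Aalen-Johansen) with other deaths as a competing event.

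The data are already planned for collection. At planning rates the all-cause version gives 6-month graft loss of at least 15% and 7%, with no cause-of-death judgement needed. The cost is SAP wording, one more estimate, and a graft-survival figure that looks less favourable. The all-cause measure will also lie close to patient survival, differing only by re-transplants, which is why the cause-specific result is worth keeping beside it.
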